## **2.d Randomization Method and Blinding**

After the consent process, the pre-test could be administered immediately or be scheduled at a different day. After pre-test, participants will be randomized immediately by a pre-programed REDCap (Research Electronic Data Capture) module. REDCap (Research Electronic Data Capture) is a secure, web-based application designed exclusively to support data capture for research studies. A blinded rater will conduct the post-test and phone follow-up.

Participants will not be blinded to which group they are in. The REDCap module uses a blocked randomization design in which gender will be stratified to ensure balanced group sizes. A block size of 2 and an allocation ratio of 1:1 based on gender. Then, based on group allocation, the occupational therapy (OT) interventionist will start either Adapted LiFE or the attention control intervention.

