### A1 Study Abstract

The purpose of this study is to pilot test the feasibility of a study design for future larger trial of Adapted LiFE among medically underserved older adults. We will evaluate if : 1) Adapted LiFE is feasible for medically underserved older adults, and 2) the study design is feasible with working randomization module and appropriate measurements.

Feasibility outcome measures include reach, acceptance, adherence, fidelity, safety, and appropriate efficacy outcome selection for balance, lower extremity muscle strength, and habit formation.

We will conduct a pilot RCT with an attentional control group. The treatment (Adapted LiFE) group (n=8) will receive 7-sessions of culturally Adapted LiFE over 12 weeks, while the attentional control group (n=8) will receive the same amount from an interventionist with a gentle flexibility program "Go4life" developed by the National Institute on Aging during intervention period.

We will recruit older adults who: are age 70 or older; self-report falls in the past 12 months; and reside in a medically underserved area. We will exclude participants who: have attention and memory impairment (Short Blessed Test score  $\geq 8$ ), are unable to stand with assistive devices, are severely depressed (The Geriatric Depression Scale  $\geq 10$ ), and have serious health conditions for which exercise is contraindicated. Paired t-tests will be used to test time effects, and independent t-tests will be used to test group effects of Adapted LiFE.

---

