## **G Statistical Analysis Plan**

### **G1 Sample Size Determination and Power**

The goal of the pilot is to test the feasibility of the Adapted LiFE for medically underserved population, and is not hypothesis testing. Thus, sample size calculation are not necessary. We select to set our sample size at 16 to evaluate feasibility and effect size for future study.

---

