## **G3 Statistical Methods**

To detect effect of intervention. Wilcoxon signed rank tests will be used to identify trends in levels of balance, muscle strength, and habit formation.

To detect effect of intervention. Wilcoxon signed rank tests will be used to identify trends in levels of balance, muscle strength, and habit formation.

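### Allocation is stratified by gender, but the only between-arm test uses neither gender nor the T1 value; if it is run on T2 scores and gender is prognostic, its intervals are too wide (minor)

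*Combined protocol and SAP*

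**What the plan says.** Section E2 2.d sets the allocation: "The REDCap module uses a blocked randomization design in which gender will be stratified to ensure balanced group sizes". It continues: "A block size of 2 and an allocation ratio of 1:1 based on gender".

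The abstract (A1) gives the only between-arm analysis: "Paired t-tests will be used to test time effects, and independent t-tests will be used to test group effects of Adapted LiFE". It does not say whether the independent t-test is run on T2 scores or on changes from T1, and it includes no covariate.

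G2 is descriptive. G3 states: "Wilcoxon signed rank tests will be used to identify trends in levels of balance, muscle strength, and habit formation". That is a paired test, so the statistical section contains no between-arm method.

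G1 gives the purpose of the sample: "We select to set our sample size at 16 to evaluate feasibility and effect size for future study". It does not say whether the effect size is raw or standardised, or by which SD. G1 also says the pilot does not test hypotheses. E1 places balance and strength measurements at both T1 and T2, and says the pilot has the same design as the future main trial.

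**The concern.** Stratified 1:1 blocks give the arms nearly the same gender mix, so a gender difference in the outcome largely drops out of the difference in means. An unadjusted t-test on T2 scores still counts that gender difference as residual noise. Its standard error then overstates the real uncertainty, and the design's gain in precision goes unreported.

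The estimate itself is not biased. What is at stake is the precision attached to the arm difference, and the SD used if a standardised effect is carried to the main trial. With 8 people per arm the intervals are wide in any case, so avoidable width matters somewhat.

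**Working it through.** The documents give no SD, gender gap, T1-T2 correlation or gender mix for this trial, and G1 makes no sample size calculation, so there is no figure of the plan to reproduce.

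**Inputs from the documents:** 16 participants, 8 per arm; blocks of 2, 1:1 within gender.

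**Assumed:** 6 men and 10 women (so 3 and 5 per arm); within-gender SD = 1; gender gap g of 0 to 1.5 SD; T1-T2 correlation r of 0.5 or 0.7; two-sided 95% intervals; no dropout.

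**Step 1. True precision.** With equal gender mix per arm the gap cancels, so SE = √(2/8) = 0.50 SD at every g.

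**Step 2. What a t-test on T2 scores reports.** The gender sum of squares per arm is 8 × (3/8) × (5/8) × g² = 1.875g². Over both arms it is 3.75g². Divided by 14 df this adds 0.268g² to the pooled variance. The mean half-width is about 2.145 × 0.50 × √(1 + 0.268g²) × 0.982, where 0.982 is the mean of an estimated SD relative to the true SD at 14 df. With gender in the model (13 df) it is 2.160 × 0.50 × 0.981 = 1.06. Simulation (20,000 trials per setting) agrees:

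| g | T2 t-test | With gender | Ratio | Coverage of t-test |
|---|---|---|---|---|
| 0 | 1.05 | 1.06 | 0.99 | 95% |
| 0.5 | 1.09 | 1.06 | 1.03 | 96% |
| 1.0 | 1.19 | 1.06 | 1.12 | 97% |
| 1.5 | 1.33 | 1.06 | 1.26 | 98.5% |

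The mix matters: at g = 1 the excess is 13% with 8 men and 8 women, but 5% with only 2 men.

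**Step 3. A t-test on change scores.** If gender shifts T1 and T2 equally, g drops out. The half-width is 1.053 × √(2(1 − r)), which is 0.82 at r = 0.7 and 1.05 at r = 0.5, whatever the gap. Simulated coverage is about 95%.

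**Step 4. T1 in the model.** Simulated half-widths:

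| g | r = 0.7, arm + T1 | r = 0.7, plus gender | r = 0.5, arm + T1 | r = 0.5, plus gender |
|---|---|---|---|---|
| 0 | 0.79 | 0.79 | 0.95 | 0.96 |
| 0.5 | 0.79 | 0.80 | 0.96 | 0.96 |
| 1.0 | 0.79 | 0.79 | 0.98 | 0.96 |
| 1.5 | 0.80 | 0.79 | 1.00 | 0.96 |

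Once T1 is in, gender gains at most about 4% and costs about 1% when it is not prognostic. T1 does most of the work.

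**Step 5. Standardised effect.** Dividing by the overall SD instead of the within-gender SD multiplies the effect by 1/√(1 + p(1 − p)g²), where p is the share of men. Here p(1 − p) = (6/16) × (10/16) = 0.234, giving 0.97, 0.90 and 0.81 at g = 0.5, 1.0 and 1.5. To see what this can do to the main trial, take a true effect of 0.5 within-gender SD, 80% power and two-sided 5%: 2 × (1.960 + 0.842)² / 0.25 = 62.8, so 63 per arm with gender adjustment. With an even mix and g = 1 the variance is 1.25 times larger: 78.5, so 79 per arm without adjustment. Either number is right for its own analysis; the error is to mix them.

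**The case against.** The strongest reply is that the harm presupposes an analysis the plan does not specify. A1 leaves open a change-score t-test, under which a constant gender difference cancels. This stands, and it makes the point conditional. The signed-rank tests in G3 are within-person, so a constant gender difference cancels there too, and they should not be faulted for omitting gender. The missing between-arm method in G3 is the larger gap.

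It is also fair to say that the documents promise no confidence interval, that the stated reason for stratifying is balance in group sizes, that the affected intervals err on the conservative side, and that the pilot's aim is feasibility. All of that stands and lowers the severity. It does not remove the need to define the comparison, since G1 makes an effect size one product of the study.

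A reader might infer three stronger things that the documents do not support:

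- That the intervals will certainly be too wide. No gender gap is given for any outcome; at g = 0 adding gender slightly widens them.
- That muscle strength is the worst case. This is plausible for force read from a dynamometer, but nothing in F2 reports a gender difference or ranks the outcomes.
- That the standardised effect will be too small. An effect on the overall SD is a legitimate marginal quantity and suits a main trial of similar mix analysed without adjustment. It misleads only if that trial adjusts for gender.

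**Conclusion.** The point holds in conditional form and is minor. The plan stratifies on gender, its only between-arm test uses neither gender nor T1, and G3 supplies no between-arm method. If the t-test is on T2 scores and gender predicts the outcome, the half-width is about 3%, 12% or 26% too wide at assumed gaps of 0.5, 1.0 or 1.5 SD with 6 men and 10 women, and coverage rises from 95% to as much as 98.5%. If the test is on change scores and gender shifts both times equally, the gender problem is nil. The larger loss is from leaving out T1 when T2 scores are compared. These sizes rest on assumed inputs and on no dropout. The raw difference is unbiased in every case, and the feasibility thresholds in C1 are untouched.

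**What to change.** In A1 and G3, state that for the continuous balance, strength and habit scores the between-arm difference at T2 will be estimated from a linear model with arm, gender (the stratification factor) and the T1 value, and reported as a raw difference with its 95% CI.

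If a standardised effect size goes to the main trial, name its SD and match it to that trial's planned analysis: the within-gender residual SD if the trial adjusts for gender, the overall SD if it does not.

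Cost: wording only, since gender and T1 are collected already. The model uses one degree of freedom for gender and one for T1 (t critical value 2.145 at 14 df, 2.160 at 13, 2.179 at 12). If gender is not prognostic, including it widens the intervals by about 1%.

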### **E1 Overview of Study Design**

The pilot study will use RCT with an attentional control design (Figure 2). The purpose of the pilot study with the same design as the future main study is to test the study protocol, estimate recruitment/retention rate, and validate tools. This study design is appropriate for a future larger study because Adapted LiFE has strong face validity, good feasibility, and minimal risk when compared with structured exercise programs for medically underserved older adults.

We will recruit 16 participants and randomize them to receive 7 sessions of home visit and 1 booster phone call one month after the last session of Adapted LiFE or attention control (AC) intervention. Once an eligible participant is screened and consented in his/her home (T0 visit), the OT interventionist will either conduct or schedule the pre-test (T1). All pre- and post-tests will be conducted in participants' homes. After T1, the OT interventionist will randomize the participants to Adapted LiFE or the attention control group. The intervention period will start immediately after randomization and consist of seven sessions over 12 weeks. Post-tests (T2) will be conducted by a blinded OT rater after the last intervention session at the participant's home. Phone follow-ups (T3) will be conducted one month after post-test by a blinded OT rater. Any additional questions from the participants will also be addressed in the phone follow-up.

Feasibility outcomes such as reach, adherence, fidelity, and safety will be evaluated throughout the study session. Efficacy outcome such as balance and muscle strength will be evaluated at pre- test (T1), and post-test (T2). Habit formation will also be evaluated at T1, T2, and 1-month after post-test via phone.

*Figure 2. Overview of the feasibility pilot study*

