## **2.g Data Collection and Follow-up for Withdrawn Subjects**

Data is directly entered into a REDCap database. REDCap servers are securely housed in an onsite, limited-access data center managed by the Division of Biostatistics at Washington University. All Web-based information transmission is encrypted. All data are stored on a private, firewall protected network. All users are given individual user IDs and passwords, and their access is restricted on a role-specific basis. REDCap was developed specifically around Health Insurance Portability and Accountability Act security guidelines and is implemented and maintained according to Washington University guidelines. Study data will be collected via tablet in the field and managed using REDCap electronic data-capture tools hosted at Washington University. REDCap is a secure, Web-based application designed to support data capture for research studies. If a participant is withdrawn from the study, his/her information will be kept in REDCap securely until the study is completed.

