### **3.d Blinding**

Participants and OT interventionist will not be blinded to the purpose of testing Adapted LiFE, and will be informed at the consent visit.

Raters will be blinded from the study. At baseline, raters will be blinded by randomizing participants after pre-test. At post-test, a blinded rater will be assigned to conduct the assessments. At one-month phone follow-up: a blinded rater will conduct the follow-up questionnaires.

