## 1.b Consent visit and Pre-test

An OT interventionist will visit all participants who meet the inclusion criteria and invite them to participate in the study. The informed consent form will be administered to all patients interested in participating in the study. During the consent process, participants will: (1) have what the study is about and what is expected of them explained in detail; (2) discuss potential problems that could interfere with participation; and (3) have their questions answered; and (4) receive a summary of the study, and contact information for the PI and study coordinator. The consent form will be signed by a witness and will be stored in the office of the PI under double locks. Participants will be advised in the consent form that there is a possibility that their medical research record, including identifying information, may be inspected and photocopied by officials of federal or state government agencies and the Washington University Human Research Protection Office (HRPO).

Written informed consent to participate in the study will be obtained before any test or measurements are performed. After the participant signed the consent form, the OT interventionist will start the pre-test immediately or re-schedule another time for pre-test.

At pre-test, a demographic questionnaire will be used to collect general information about the participant. A set of questionnaires and performance-based assessment will be conducted to evaluate participants attitude and abilities. After pre-test, participants will be randomized in the field.

Table. Materials and assessments for consent and pre-test

Construct	Assessments	Time
Primary endpoints		
Static balance	

Four-Stage Balance Test*

Center of pressure (CoP) path measured by BTracks Balance Board

	T1, T2
Dynamic balance	

Timed tandem walk*

Short Physical Performance Battery-Balance Test (SPPB)*

Berg Balance Scale (BBS)

	
Muscle strength	

Lower extremity muscle strength measured by dynamometers*

	
Secondary endpoints		
Habit formation	

Self-Reported Habit Index (SRHI)

	T1, T2 , T3
Balance efficacy	

The Activities-specific Balance Confidence

	T1, T2, T3

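### With one fixed block size of 2 within gender, an OT who knows it and has seen the earlier same-gender allocations can deduce up to 7 or 8 of the 16 arms before the pre-test

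*Combined protocol and SAP*

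**What the plan says.** Section 2.d states that the REDCap module "uses a blocked randomization design in which gender will be stratified to ensure balanced group sizes", and then gives the detail: "A block size of 2 and an allocation ratio of 1:1 based on gender". No other block size is mentioned. No section says that sizes vary, that they are kept from the field staff, or that an independent person makes the assignment.

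The same role appears at each step:

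- **Invitation.** Section F 1.b has an OT interventionist visit and invite eligible people. Section 2.c instead has a trained staff member obtain consent.
- **Pre-test.** F 1.b says that "the OT interventionist will start the pre-test immediately or re-schedule another time for pre-test". E1 leaves open whether the OT does the test or only arranges it.
- **Randomisation.** E1: "After T1, the OT interventionist will randomize the participants to Adapted LiFE or the attention control group".
- **Treatment.** Under 2.d the OT interventionist then starts the assigned programme.

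Baseline blinding rests on one mechanism, in 3.d: "At baseline, raters will be blinded by randomizing participants after pre-test". The post-test (T2) and the phone follow-up (T3) are assigned to a blinded rater.

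**The concern.** Randomising after the pre-test protects the pre-test only if the coming arm cannot be foreseen. With a single block size of 2, half of each completed pair can be foreseen by anyone who knows the block size and the running allocations in that gender. The person best placed to know them is the OT who randomised and treated the earlier participants.

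Two routes are open:

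- **T1 scoring.** The Berg scale, the SPPB and dynamometry are scored or administered by the tester. T1 scores enter the pre-post signed-rank tests in G3 and the effect size in G1: "We select to set our sample size at 16 to evaluate feasibility and effect size for future study". They would also enter the independent t-tests in A1 if those use change from T1, which A1 does not specify. A blinded rater at T2 cannot undo an influence on T1.
- **The consent visit.** If the OT makes the invitation, the next arm may already be known at that point. That fails when an earlier same-gender participant has consented but is not yet randomised.

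A1 also makes a working randomisation module something the pilot is to test, and E1 says the pilot shares the design of the main study. A predictable scheme could be carried forward.

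**Working it through.** **Inputs.** 16 participants, 8 per arm (A1, E1); block size 2, ratio 1:1, stratified by gender (2.d). The gender mix is not given; 60% women is assumed, with 50% to 80% as the range. The number of OTs is not given: F2 uses the plural, other sections the singular.

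**1. The plan's own figure, 8 and 8.** Let w be the number of women.

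- w even: every block is complete and the split is exactly 8:8.
- w odd: each stratum ends with one unpaired participant. The split is 8:8 with probability 0.5, otherwise 7:9.

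Under a binomial gender mix, w is odd with probability [1 − (1 − 2p)^16]/2, which is essentially 0.5 for p from 0.5 to 0.8. So P(8:8) = 0.5 × 1 + 0.5 × 0.5 = 75%. The planned arm sizes are reproduced, exactly or within one participant per arm.

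**2. Arms deducible with one OT, or shared knowledge.** The count is floor(w/2) + floor((16 − w)/2): 8 when w is even and 7 when w is odd, with no other value for any gender mix. The mean is 0.5 × 8 + 0.5 × 7 = 7.5 of 16 (47%).

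**3. Best guess.** The remaining arms are guessed at 50%: 7.5 + 8.5 × 0.5 = 11.75 of 16 (73%), against 8 of 16 by chance.

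**4. Two OTs who do not share.** If participants fall to them at random, the same OT handles both members of a pair half the time: 8/2 = 4 or 7/2 = 3.5 pairs. The arrangement matters. With 8 men and 8 women, the count is 0 if the OTs alternate within each gender and 8 if one sees all the men and the other all the women. Such an OT must also know that the block is open, so 3.5 to 4 is on the high side for that set-up.

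**5. Block sizes drawn at random from 2 and 4, equally likely.** All allocation sequences in each stratum were enumerated. The guesser knows the set of possible sizes but not the sizes drawn, and updates after each allocation. An arm counts as certain when its probability is 0 or 1. That happens only after one arm leads by two within a gender, because the block must then be a 4 and its last two places are fixed.

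| 60% women | Block 2 | Random 2/4 |
|---|---|---|
| Arms certain, of 16 | 7.50 | 1.48 |
| Best guess right, of 16 | 11.75 (73%) | 11.24 (70%) |
| P(8:8) | 75.0% | 64.8% |
| P(7:9 either way) | 25.0% | 34.9% |
| P(6:10 either way) | 0 | 0.3% |

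From 50% to 80% women these figures move by less than one percentage point. If both strata are exactly 8, block 2 gives 8 certain, 12.0 right and P(8:8) 100%; random 2/4 gives 1.5 certain, 11.4 right and P(8:8) 81%.

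**6. Price of a 7:9 split.** Variance of a group difference relative to 8:8: (1/7 + 1/9)/(1/8 + 1/8) = 1.016, or 1.6% more. The standard error rises by 0.8%.

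**The case against.** The strongest case against a change has four parts.

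- **The conditions are not established.** The documents do not say that OTs know the block size, and F2's plural suggests more than one OT. REDCap access is limited by role (2.g: "their access is restricted on a role-specific basis"), which may hide the allocation list. This stands: 7 or 8 is an upper case. But hiding the list does not prevent inference from allocations the OT has made, and no passage describes a safeguard against it.
- **The gain in guessing is small.** Varying the block size removes about half a correct guess in 16 (11.75 to 11.24). This also stands. What falls sharply is certainty.
- **Block 2 serves a stated aim,** balanced group sizes, which matters at 16 participants. True, and the change gives up some of it.
- **This is a feasibility pilot,** which G1 says does not test hypotheses. Recruitment, retention, acceptance, adherence, fidelity and safety do not use T1 scores, and block size could be changed when the main trial is programmed. This stands and limits the weight of the point.

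A reader might infer that the OTs in this trial will know half the allocations, or that baseline scores or enrolment are biased. The documents support neither. They show that arms can be predicted under certain conditions, not that those conditions hold or that anyone would act on them.

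**Conclusion.** The point holds as a cheap improvement. Under the stated scheme, an OT who knows or infers the block size and has seen all earlier same-gender allocations can deduce at most 7 or 8 of 16 arms before T1, and possibly at the consent visit. The figure rests on one OT or shared allocations; for two OTs who do not share it is roughly 3.5 to 4, with participants falling to them at random. The baseline blinding claimed in 3.d is therefore not assured where the OT tests at T1. E1, 3.d and F 1.b do not agree on who does that.

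The consequence is confined to T1 and possibly consent. T2 and T3 are blinded, no bias is shown, and the effect on the feasibility outcomes is small. Nor should a reader take varying block sizes as securing baseline blinding: they reduce prediction but do not remove it.

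**What to change.** Before enrolment:

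1. Load a REDCap allocation table with block sizes drawn at random from 2 and 4 within gender. Keep the sizes in a separate file.
2. In 2.d, replace the block-size sentence with: *Permuted blocks of randomly varying size, stratified by gender, ratio 1:1; block sizes are not disclosed to interventionists or raters.*
3. In 3.d, replace the baseline sentence with: *Baseline tests are completed before randomisation. Full baseline blinding is not claimed where the tester knows earlier allocations.*
4. Reconcile E1, 3.d and F 1.b on who tests at T1.

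The work is one new table and a few amended sentences. The statistical cost is less exact balance: P(8:8) falls by about 10 percentage points (19 if both strata are exactly 8), nearly all of it to 7:9, with the 1.6% rise in variance shown above.
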